8.4 Microbiome samples

Stool collection for microbiome analysis will be collected at Baseline, end of radiation, C4D1 and C7D1. to explore changes of the microbiome during ICB. Appendix 2 describes the protocol for stool collection.

9 Measurement of Effect

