10.2 Regulatory Considerations

All protocol amendments and consent form modifications will be made by the Principal Investigator. *Bristol-Myers Squibb* will have the opportunity to review and approve the changes prior to submission of these changes to the local IRB.

11 Statistical Considerations

The primary endpoint of this study is response rate. The trial design is a single arm, single-center, Simon optimal two-stage design. Patients will be evaluated for response at 12 weeks (84 days \pm 7 days). Patients will be enrolled in two stages with 13 patients in the first stage, and potentially an additional 13 patients in the second stage. The decision to enroll patients into the second stage will depend on the number of responses observed in the first stage, as described below.

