11.1 Sample Size/Accrual Rate

As mentioned, a Simon's two-stage optimal design [Simon, 1989] will be used. The null hypothesis that the true response rate is 20% will be tested against a one-sided alternative. If there are 3 or fewer responses in these 13 patients, the study will be stopped. Otherwise 13 additional patients will be accrued for a total of 26 patients. The null hypothesis will be rejected if 10 or more responses are observed in 26 patients. This design yields a one-sided type I error of 0.025 and power of 60% when the true response rate is 40%. The target sample size is 26 evaluable patients and up to 30 patients (4 extra patients) will be accrued to account for non-evaluable patients or patients who withdraw prior to evaluation.

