11.4 Analysis of Correlative Endpoints

11.4.1 Microbiome

11.5 Statistical analysis of microbiome and metagenome composition

Statistical analysis of microbiome and metagenome composition will be performed in the R statistical programming environment⁵⁶ using package *phyloseq*⁵⁷, which incorporates and builds upon community ecology packages such as *ade4* and *vegan* and employs the flexible graphic system *ggplot2*, to easily visualize complex data relationships. For 16S data, we will evaluate the adequacy of sequencing efforts using rarefaction plots. Alpha diversity index for each will be characterized through dominance, equitability, richness, evenness. The diversity metrics will be calculated at Operational Taxonomic Unit (OTU) and higher taxonomical levels to best characterize the community structure. We will test for associations of each of these alpha diversity metrics with the time relative to radiation exposure, using one-way ANOVA after even-sampling the observations to a depth cut-off maximizing the number of samples and depth. In addition, rank-abundance plots will be used to visualize differences in abundance of dominant taxa in the clinical and phenotypic groups. We will utilize skyline plots to visualize the patterns of community structure in terms of relative abundances in the collected samples between before and after the radiation treatment or between case and control samples. Similarly, for metagenomic data, skyline plots will be used to reveal functional compositions of the samples. Heat-maps will be plotted to visualize clustering patterns in the data.

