Univariate analyses. To circumvent instabilities associated with rare species, which are difficult to detect uniformly in all samples, we will focus our primary univariate analyses only on highly abundant taxa, i.e. those present at 1% or more relative abundance across all specimens. This approach will also help to reduce multiple comparison-related Type I-error inflation, which will be formally controlled by false discovery rate (FDR)⁵⁸. The differences in presence or absence of specific taxa and functional categories will be assessed by χ^2 -test at all taxonomical levels. *Paired-Sample Wilcoxon Signed Rank Test* will be used to establish the differences in relative abundance of taxa between before and after the radiation treatment or between paired samples. Depending on the dynamics observed, subsequent analyses may focus on less abundant taxa, and at higher depth, as indicated above.

Multivariate analyses. Multivariate association of the entire microbiome/metagenome with clinical and phenotypic factors will be examined with Principal Coordinate Analysis (PCoA) on Jensen-Shannon, weighted and unweighted Unifrac, and χ^2 (correspondence analysis) distances. Likewise, these distances will be used to build non-parametric multivariate Analysis of variance (ANOVA) models (ADONIS)⁵⁹ to allow for simultaneous measurement of univariate and interaction effects of the clinico-phenotypic variables on the microbiome. Starting with the microbiota and metagenomic features significantly different in univariate analyses, we will use the dimension-reduction method, canonical correlation analysis (CCA) to identify the bacteria taxa which are related radiation treatment, according to benchmarked methodologies of our prior studies^{54,60}. We will utilize a phylogenetic structure-constrained penalty function to impose phylogenetic relationships among bacteria on the model selection⁶¹.

Longitudinal analysis: We will study the evolution of microbiome over time and how that evolution is associated with the radiation treatment. The relative abundances at each taxonomical level will

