be first normalized by log-ratio transformation ⁶². Then the transformed relative abundance of each individual taxa at multiple time points will be fitted by the linear mixed model along with the time effect and all subject-specific characteristics as the independent covariates. For the nonlinear trend, we will combine the nature splines with linear mixed model in the data analysis. The same model will be applied on the indices calculated in the ecology microbial analysis. For the joint analysis of more than one taxon, we will use MCMCglmm R package to implement the multivariate generalized linear mixed model. This package gives a large flexibility in analyzing correlated multiple longitudinal response by allowing different types of covariance structure ⁶³.

12 Adverse Event Reporting Requirements

CTCAE Version 4.0 will be used for tracking the Adverse Events in this study.

Adverse event (AE) monitoring and reporting is a routine part of every clinical trial. The investigator will be required to provide appropriate information concerning any findings that suggest significant hazards, contraindications, side effects, or precautions pertinent to the safe use of the drug or device under investigation.

Safety will be monitored by evaluation of adverse events reported by patients or observed by investigators or research staff, as well as by other investigations such as clinical laboratory tests, x-rays, electrocardiographs, etc.

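### Section 11.5 tests presence or absence of taxa with an ordinary chi-square test and names no comparison; if it is used before versus after radiation, it ignores the pairing and usually loses power

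*Combined protocol and SAP*

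**What the plan says.** The univariate paragraph of section 11.5 has two sentences on testing. The first reads "The differences in presence or absence of specific taxa and functional categories will be assessed by" a chi-square test, at every taxonomic level. It names no groups, no visits and no paired form. The second gives a paired-sample Wilcoxon signed rank test, which "will be used to establish the differences in relative abundance of taxa between before and after the radiation treatment or between paired samples". The p-values are to be controlled by false discovery rate (FDR).

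The design is described elsewhere. Section 8.4: "Stool collection for microbiome analysis will be collected at Baseline, end of radiation, C4D1 and C7D1". Opening of section 11: "The trial design is a single arm, single-center, Simon optimal two-stage design". Section 11.1: "The target sample size is 26 evaluable patients and up to 30 patients".

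The longitudinal paragraph of section 11.5 does handle repeated measures, but for another quantity: "the transformed relative abundance of each individual taxa at multiple time points will be fitted by the linear mixed model". The same model is extended to the ecology indices. No paired or mixed method is assigned to presence or absence.

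**The concern.** In a single-arm trial with serial stool samples, any before/after comparison is made within patients. A chi-square test on the before and after proportions assumes two independent sets of patients. A taxon or function carried at baseline is likely to be carried later as well, so the test overstates the variance of the change. It then rejects too rarely and can miss real shifts in carriage.

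The missed shifts would also be lost later. The p-values enter the FDR step, and the canonical correlation analysis starts from features significant in the univariate analyses. The authors wrote pairing into the abundance test but not into this one, so the text leaves open whether the omission was intended.

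**Working it through.** The plan gives no power or error figure for this test, so there is none to reproduce.

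**Inputs**
- Pairs: 26 (section 11.1 target), or 13 if the trial stops after stage 1.
- Level: two-sided 0.05 (assumed; the plan states no per-test level).
- Within-patient correlation of presence, phi: not in the documents. Assumed 0.3 to 0.5, with 0 as a check.
- Carriage: not in the documents. Assumed 50% with no change, 35% to 65%, and 80% to 95%.

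**Step 1: direction, by hand.** With equal carriage p at both times, the variance of the difference in proportions is 2p(1−p)(1−phi)/n. The chi-square test uses 2p(1−p)/n, so its z-statistic has standard deviation √(1−phi), not 1. The approximate true type I error is 2·[1 − Φ(1.96/√(1−phi))]:
- phi 0.3: 1.96/0.837 = 2.34, giving 1.9%.
- phi 0.5: 1.96/0.707 = 2.77, giving 0.6%.

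**Step 2: exact enumeration.** With carriage p1 before and p2 after, P(both) = p1·p2 + phi·√(p1(1−p1)p2(1−p2)); the other cells follow by subtraction. For 35% to 65% at phi 0.5:
- both: 0.2275 + 0.5 × 0.2275 = 0.34125
- before only: 0.35 − 0.34125 = 0.00875
- after only: 0.65 − 0.34125 = 0.30875
- neither: 0.34125

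Every possible paired 2×2 table is weighted by its multinomial probability and tested with:
- Chi-square: 2n(x1−x2)²/[t(2n−t)], where x1 and x2 are the carriers before and after and t = x1+x2.
- McNemar, asymptotic: (b−c)²/(b+c), where b and c are the discordant counts.
- McNemar, mid-p: 2·P(X ≤ min(b,c)) − P(X = min(b,c)), with X binomial(b+c, 1/2).

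Probability of rejection:

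| Pairs | Carriage | phi | Chi-square | McNemar asymptotic | McNemar mid-p |
|---|---|---|---|---|---|
| 26 | 50%, no change | 0.3 | 1.8% | 4.3% | 4.1% |
| 26 | 50%, no change | 0.5 | 0.6% | 4.7% | 3.4% |
| 26 | 35% to 65% | 0 | 56.8% | 55.9% | 55.8% |
| 26 | 35% to 65% | 0.3 | 58.5% | 71.4% | 71.1% |
| 26 | 35% to 65% | 0.5 | 59.7% | 91.5% | 88.5% |
| 13 | 35% to 65% | 0.3 | 38.5% | 42.1% | 32.1% |
| 13 | 35% to 65% | 0.5 | 35.4% | 55.3% | 34.4% |
| 26 | 80% to 95% | 0.3 | 36.9% | 47.9% | 33.3% |

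The exact (non-mid-p) McNemar test is weaker. For 35% to 65% with 26 pairs it has 61% power at phi 0.3 and 79% at phi 0.5.

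**Step 3: other uses of the same sentence** (simulation, 26 patients, assumed split of 10 against 16).
- Patient groups at one visit: type I error 4.7% to 4.9%, so the chi-square test is valid.
- Patient groups with all four visits pooled as if independent: 16%, 22% and 27% at within-patient correlation 0.3, 0.5 and 0.7. The error is then in the opposite direction.

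**The case against.** The strongest reply is that the sentence never says before versus after. That phrase belongs to the Wilcoxon sentence. Section 2.6.1 aims at associations with response, and section 11.5 also speaks of comparisons "in the collected samples between before and after the radiation treatment or between case and control samples". For responders against non-responders at one visit the chi-square test is sound. This stands. A reader might infer that the plan prescribes an invalid test and that real changes will be missed; the text supports this only under the before/after reading. If the group reading is the right one, however, the plan has no before/after test of presence or absence at all, so the sentence needs completing either way.

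A reader might also infer excess false discoveries. On the before/after reading the p-values are conservative, so the cost under FDR is power. False positives would rise only if visits were pooled across patient groups, and nothing in the documents says they will be.

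The size is also open to challenge, and this stands too. Phi is assumed. Twenty-six complete pairs is optimistic, because it needs both home-collected samples from every evaluable patient. A stop at 13 is likely if the treatment does nothing: P(3 or fewer of 13) at a 20% response rate is 0.75. The primary univariate analyses are limited to taxa at 1% or more relative abundance across all specimens. If that means in every specimen, presence never varies for those taxa and the test is empty for them. Functional categories and the later work on rarer taxa would remain, although the methods in section 2.6.1 describe only 16S sequencing.

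Finally, within-patient change in abundance is already covered by the Wilcoxon test and the mixed models. That limits the consequence but does not supply a method for presence or absence.

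**Conclusion.** The point holds as a gap in specification with a conditional statistical cost. The test for presence or absence has no stated comparison, and no other text assigns a paired or mixed method to that outcome.

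Used before versus after, the chi-square test is too conservative whenever within-patient correlation is positive. At phi 0.3 to 0.5 with 26 pairs and mid-range carriage it gives up roughly 13 to 29 percentage points of power against mid-p McNemar (71.1 − 58.5 = 12.6; 88.5 − 59.7 = 28.8). The advantage vanishes near phi 0. Mid-p is slightly less powerful than chi-square in the 13-pair cases and in the 80% to 95% case shown. All these figures rest on assumed correlation and carriage.

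The importance is low: the analysis is exploratory, and neither the primary endpoint nor any stopping decision depends on it.

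**What to change.** Rewrite the sentence in section 11.5 so that it names the comparison and the matching test:
- **Before versus after:** McNemar's test (asymptotic or mid-p, chosen in advance) on a named pair, baseline against end of radiation.
- **Across all four visits:** Cochran's Q, or a logistic mixed model with a patient random intercept.
- **Patient groups:** one sample per patient at a named visit (Fisher's exact or chi-square), or the same mixed model.
- **Multiplicity:** apply the FDR procedure to the p-values from these tests.

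This takes a few lines of text and different function calls, with no new data. The cost is that patients missing one sample of a pair drop out of the McNemar comparison, and in small samples mid-p may bring no gain in power.

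### The canonical correlation analysis for radiation-related taxa starts from taxa already screened on the same contrast, with no validation stated that repeats the screen, so any strength of association it reports will be optimistic

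*Combined protocol and SAP*

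**What the plan says.** All quotes are from Section 11.5 of the combined protocol and SAP.

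- **Abundance screen.** A paired Wilcoxon signed-rank test "will be used to establish the differences in relative abundance of taxa between before and after the radiation treatment or between paired samples".
- **Presence/absence screen.** "The differences in presence or absence of specific taxa and functional categories will be assessed by" a chi-square test.
- **Candidates and multiplicity.** The primary univariate analyses cover abundant taxa, "those present at 1% or more relative abundance across all specimens". Type I error inflation is addressed by a procedure "which will be formally controlled by false discovery rate (FDR"). No FDR level is given.
- **CCA.** "Starting with the microbiota and metagenomic features significantly different in univariate analyses, we will use the dimension-reduction method, canonical correlation analysis (CCA"). Its purpose is "to identify the bacteria taxa which are related radiation treatment, according to benchmarked methodologies of our prior studies".
- **Penalty.** "We will utilize a phylogenetic structure-constrained penalty function to impose phylogenetic relationships among bacteria on the model selection".

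Stool is collected in one series of four time points per patient (Section 5.1 footnote d, Section 8.4, Appendix 2). Section 11.1 plans 26 evaluable patients, up to 30 accrued, and 13 if the trial stops after stage 1. The Protocol Summary lists the microbiome work as exploratory.

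Section 11.5 does not mention a hold-out set, cross-validation, permutation of the full procedure or a correction for selection. It also does not say which CCA statistic will be reported.

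**The concern.** The screen and the CCA address the same question with the same data. The screen keeps taxa whose before/after difference happens to be large in these patients. The CCA then measures how strongly those taxa separate before from after in the same patients. Chance differences that helped a taxon through the screen are counted again in the canonical correlation and its loadings. A p-value that treats the selected set as fixed ignores that the set was chosen for its difference.

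FDR control governs the expected share of false taxa on the list. It does not correct the size of the association estimated for the taxa that pass.

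What is at stake is interpretation. A multivariate result that agrees with the univariate list could be read as confirmation, and Section 2.6.1 presents these data as a step towards using the microbiome therapeutically. An overstated association could be carried into later work.

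**Working it through.** The plan gives no expected correlation, power or alpha for this CCA, so there is no stated figure to reproduce. The check is by Monte Carlo simulation.

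**Inputs from the documents.** n = 13, 26 and 30 (Section 11.1); paired Wilcoxon screen under FDR control; CCA against radiation (Section 11.5).

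**Assumptions, not in the documents.** 30 taxa in the main setting (20 and 60 as a range); independent, normally distributed taxa on a transformed scale; within-patient correlation 0.5; Benjamini-Hochberg (BH) at 5% (20% as a range); unpenalised CCA. The phylogenetic penalty was not simulated.

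**Procedure.**
1. Generate before and after values for each patient.
2. Screen with the paired Wilcoxon test and BH.
3. Run the CCA of the selected taxa on the before/after label. With one binary variable this is the multiple correlation.
4. Apply the fitted weights to new patients.
5. Separately, refit the same selected taxa in fresh patients at the same n. This keeps ordinary small-sample fitting but removes the reuse of the screening data.

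All results are conditional on at least one taxon passing.

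**Main setting: 30 taxa, 3 shifted by 0.6 SD, BH 5%.**

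| n | In-sample | Refit in fresh patients | Fitted weights in new patients |
|---|---|---|---|
| 26 | 0.46 | 0.36 | 0.34 |
| 13 | 0.51 | 0.29 | 0.26 |

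- n = 26: total gap 0.46 − 0.34 = 0.12; part due to selection 0.46 − 0.36 = 0.10.
- n = 13: total gap 0.51 − 0.26 = 0.25; part due to selection 0.51 − 0.29 = 0.22. A taxon passes in only about 20% of these data sets.

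A second, separately written simulation gave 0.46 against 0.34 at n = 26 and 0.54 against 0.28 at n = 13, with refits of 0.37 and 0.31.

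**Other effect sizes: 5 of 20 or 60 taxa shifted, BH 5%.**
- n = 26, shift 0.4 SD: 0.40–0.41 in sample against 0.20–0.23 in new patients.
- n = 26, shift 0.8 SD: 0.66–0.70 against 0.57–0.62.
- n = 13, both shifts: 0.49–0.76 against 0.17–0.48.

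The bias is upward in every setting and proportionally largest when effects are weak or n is small.

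**No taxon truly changed.**
- With 30 taxa and BH 5%, some taxon passes in about 5% of data sets. With 20 or 60 taxa the figure is about 0–4%; at BH 20% it is 7–17%.
- When a taxon does pass at BH 5%, the mean in-sample correlation is 0.30–0.42 and the new-patient value is about 0.
- A within-pair permutation test that holds the selected set fixed was then significant at 5% in every run tested.

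**Does repeating the screen cure it?** With 26 patients, 20 taxa and no true change, rerunning screen plus CCA inside each within-pair permutation rejected in 3.2% of data sets with a BH 5% screen, and in 4.4% with an unadjusted screen. Nominal is 5%. CCA on one or three pre-specified taxa with no screen rejected in 3.7–4.7%. The excess therefore comes from screening and testing on the same samples.

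**The case against.** Several points on the other side stand.

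- **FDR control is planned.** A reader might infer that false associations will be common. With an unadjusted screen at p < 0.05 some taxon would pass in 63–96% of null data sets, but that is not the planned procedure. Under BH 5% the figure is about 5%.
- **No CCA statistic is promised.** The stated purpose is "to identify the bacteria taxa which are related radiation treatment". The plan names no canonical correlation, loading test or p-value for reporting and does not call the CCA independent support. The point therefore applies to any such figure if it is reported.
- **Ordinary overfitting contributes.** With the three true taxa pre-specified and no screen, the CCA still gave 0.49 in sample against 0.44 in new patients at n = 26, and 0.53 against 0.42 at n = 13. Selection is most of the gap in the main setting, not all of it.
- **At n = 26 the in-sample value is not above what the full true set could give.** With all three taxa and ideal weights the population value is √(D²/(D²+4)), D² = 3 × 0.6² = 1.08, so √(1.08/5.08) = 0.46. This equals the in-sample 0.46. However, the screen often misses true taxa, and the fitted combination actually reported achieves only 0.34 in new patients.
- **Screening before modelling is defensible.** Unpenalised CCA on all 30 taxa at n = 26 gave 0.79 in sample against 0.22 in new patients, worse than the screened version. The penalised CCA without a screen was not simulated, so the documents and the check do not show that the screen should go.
- **The penalty may drop or down-weight screened taxa.** It is too strong to say that the CCA cannot fail to agree with the univariate list. But the penalty acts after the screen and does not undo it.
- **The cited prior methods may include validation.** Their content is not in the documents. One can say only that none is stated.
- **Unscreened analyses are also planned:** principal coordinates, ADONIS and longitudinal mixed models.

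**Conclusion.** The concern holds in a limited form. As written, the CCA starts from taxa chosen on a contrast that it then re-estimates in the same samples, and no validation repeating the screen is stated. That the same samples are used is inferred from the single stool series and the absence of any split. Starting from the significant features is plainly read as using those features, although other taxa are not expressly barred.

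Any correlation, loading or p-value obtained this way is optimistic. Under the stated assumptions the overstatement is about 0.12 on the correlation scale with 26 patients and about 0.25 with 13, in the data sets where something passes. The exact size depends on the number of taxa, effect size, FDR level, dependence between taxa and the penalty; the direction did not change in any setting run.

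The documents do not support the stronger readings that false findings will be frequent, that the whole gap is selection, or that the screen itself is a mistake. This is a minor point on an exploratory analysis. It does not affect the primary endpoint or any stopping rule.

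**What to change.** Add to the multivariate part of Section 11.5:

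1. The univariate screen may be kept or dropped. If kept, the screen and the penalised CCA are repeated together inside each fold of a patient-level cross-validation, and inside each within-patient permutation if a p-value is given.
2. The canonical correlation reported is the cross-validated one.
3. Otherwise the CCA is labelled descriptive, and no p-value or strength of association is reported from it.
4. State the FDR level of the screen. If the cited prior methods already validate the full procedure, a sentence saying so settles the point.

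The cost is some analysis code and, most likely, a smaller reported correlation. No patient, sample or visit is affected.
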